Table 1. Outcome Variables in Pilot Study	
	Intervention (n = 7)^a
	Mean (SD)
CG Self-efficacy (Total Score)	
Baseline	143.0 (23.5)
4 weeks after RT	146.4 (24.1)
CG Self-efficacy for managing medical information	
Baseline	23.1 (2.0)
4 weeks after RT	23.6 (2.9)
CG Self-efficacy for caring for the care recipient	
Baseline	47.9 (4.3)
4 weeks after RT	50.6 (3.6)
CG Self-efficacy for caring for oneself	
Baseline	31.4 (9.1)
4 weeks after RT	33.1 (8.6)
CG Self-efficacy for managing difficult situations	
Baseline	40.6 (9.6)
4 weeks after RT	39.1 (11.5)
Global Mental Health (Tscore)	
Baseline	49.4 (6.6)
4 weeks after RT	49.8 (4.9)
Global Physical Health (Tscore)	
Baseline	44.9 (8.2)
4 weeks after RT	46.9 (6.3)
Anxiety (Tscore)	
Baseline	57.8 (9.5)
4 weeks after RT	53.4 (11.3)
Depression (Tscore)	
Baseline	51.3 (8.3)
4 weeks after RT	53.9 (4.7)
Unplanned hospital admissions	2 patients
Interrupted radiation therapy	0 patients

^aOne CG did not return surveys at 4 weeks and was dropped from the analysis.

definitive treatment.⁶⁵ Results confirmed that this posttreatment transition is a “teachable moment” for family members, as CGs in the study reported low levels of physical activity, yet thought about making health behavior changes, expressed strong intentions for engaging in physical activity, and were receptive to talking with a nurse about their physical and emotional health. CGs had higher distress levels than patients at the completion of treatment ($U = 724.5, z = -1.95, p = .05$). Stress and emotional concerns were the most frequently reported barriers to improving CG health. The results identified the need for a self-care aspect to the intervention and support the need to target CG distress during treatment.

Study of Health Management in Patients and CGs During Cancer Treatment ([name], PI) was a descriptive, longitudinal study of activation in 42 CGs and 62 patients newly diagnosed with colorectal cancer.⁸⁴ Using linear mixed-effects models, we found that lower CG self-efficacy for managing one’s own health was associated with higher levels of CG depression ($p = .003$) and anxiety ($p = .021$), as well as higher levels of patient symptom distress ($p = .046$). As a result of this study, we designed the intervention to include an assessment of CG emotional distress during the initial few minutes of each

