We estimate, based on the annual Cancer Registry data, that 131 patients with stage I, II, III rectal, anal, and esophageal cancers; stage III NSCLC; and stage I-IV A/B HNC will be receiving radiation therapy at the three study sites of the Cancer Center. Approximately 10% of these patients will not meet our eligibility criteria (e.g., no family CG), resulting in 118 potential participants annually. Based upon our current pilot study, *Building Family CG Skills Using a Simulation-Based Intervention for Care of Patients with Head and Neck Cancer*, we expect a CG refusal rate of 40%. Therefore, we project to enroll 71 CGs per year or 5 per month. We plan to enroll subjects for 36 months, resulting in an enrollment of 180 subjects over the course of the study. We will allow for a 10% dropout rate, resulting in 162 subjects for the final analysis. The estimated 10% attrition rate is based on a current caregiver intervention study in the Cancer Center, in which the rate is 9.7% (NR015464, [name] PI).

While 40% is a high refusal rate, it is consistent with other intervention studies that aimed to enroll patient-caregiver dyads.^{2,3,90} In addition, the use of incentives has been found to reduce the refusal rate in this CG population, and thus, we will offer a \$100 incentive to all CGs for participation in the study. We will also seek IRB approval to collect additional information from CGs who refuse, including whether the CG is working and/or providing care to other individuals, which were common reasons for refusal in the pilot study. Lastly, we will monitor the refusal rate monthly. If the refusal rate is greater than 40% for more than 4 months, we will consider revising our strategies and seek other sites. We will offer a \$40 incentive to all patients for participation in the study.

For the extension period, with the increased number of study sites we project to enroll 6 caregivers per month. We plan to enroll subjects for an additional 16 months, resulting in 96 subjects over the course of the extension project. We project that the parent study will enroll a total of 148 subjects. Adding the 96 subjects in the extension project will result in a total sample size between the parent study and extension project of 244. With an estimated dropout rate of 12%, the sample for the final analysis will be 214 dyads.

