6.0 STATISTICAL ANALYSIS

6.1 Primary and secondary endpoints.

The primary endpoint is difference in caregiver anxiety between the intervention and control groups at 20

weeks post-radiation treatment. Secondary endpoints are caregiver anxiety at the end of radiation treatment and 4 weeks post treatment; caregiver depression, HRQOL, and fatigue at the end of treatment and 4 weeks post-treatment; and patient HRQOL at the end of treatment and 4 weeks post-treatment.

6.2, 6.7, 6.8 Statistical Design, Power, Analysis plan, & Missing data.

An intent-to-treat analysis is planned. Before carrying out inferential statistical procedures, exploratory data analysis will be performed: all variable distributions will be examined and descriptive summary statistics will be provided: including means, standard deviations, and ranges for continuous variables, as well as percentages and frequencies for categorical variables, will be provided to describe the study sample. Variable transformations will be made in cases where distributions are skewed, or otherwise fail to meet the assumptions for analyses; nonparametric procedures will be used where transformations would be inappropriate. Plots will be used to describe the data and identify outliers and influential observations.

Aim 1

Analysis. The primary analysis for Aim 1 will be to compare the control and CG intervention arms with respect to CG anxiety at T4 (20 weeks postradiation treatment). A linear mixed model repeated measures analysis will be used to obtain mean changes from baseline in anxiety scores at Times T2, T3, and T4, using baseline anxiety as a covariate, also adjusting for covariates described in Table 4. A contrast of means will be constructed to compare arms with respect to change in anxiety at T4 (primary analysis) at the 0.05 significance level. In addition, the baseline characteristics of the two treatment groups will be compared using appropriate 2-sample tests for continuous or binary outcomes, and in a secondary analysis, characteristics found to differ between groups at baseline will be adjusted for in the linear mixed model. A secondary analysis will test for differences between groups at the other postbaseline time points, using the Tukey method to control the familywise error rate on a per outcome basis. Other CG outcomes will be compared between groups using a similar approach.

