Power. With 180 subjects randomized and a 10% dropout rate, the sample size for the primary analysis will be 162 CGs (81 per arm). Assuming a correlation of 0.50 between CG anxiety scores at baseline and T4, when adjusting for baseline anxiety, a difference in means of 0.36 standard deviations (*SDs*) can be detected with 80% power using a 2-sided test with significance level 0.05, where *SD* is the within-group standard deviation of anxiety scores at Time T4. Here, adjustment for baseline anxiety reduces the detectable effect size from 0.41 to 0.36. This effect size (Cohen's *d*) is intermediate between a "small" (0.2) and "moderate" effect size, as defined by Cohen,¹⁰⁶ and is close to the pooled estimate of 0.29 from a meta-analysis of interventions (psychoeducational, skills training, and therapeutic counseling) with family CGs of cancer patients.² For other outcomes, there is 80% power to detect effect sizes of 0.41 *SDs* with a 2-sided test, significance level 0.05.

Aim 2

Analysis. This aim is to measure the effect of the intervention, as compared to a control group, on patient outcomes (HRQOL, interrupted treatment course) and healthcare utilization outcomes (unplanned hospital admissions, unplanned emergency room visits, and unplanned IV fluid use). Most outcomes will be count variables enumerating the cumulative numbers at T2, T3, and T4, which can be analyzed using Poisson regression methods implemented as generalized linear models, possibly allowing for overdispersion. Zero-inflated Poisson or negative binomial models^{107,108} will be considered if the data indicate a higher frequency of zeros than predicted by a Poisson model. HRQOL, a continuous measure, will be analyzed using a linear mixed model with repeated measures at T1, T2, T3, and T4. We will analyze the effect of the intervention on HRQOL across diagnoses using the common FACT subscales and will describe the symptom experience within each diagnostic group using the cancer-specific FACT subscale.

Power. From our pilot study, in the control group we expect means of 0.29 and 0.25 for the number of unplanned missed days and number of unplanned hospital admissions, respectively. In a Poisson regression model, sample sizes of 81 patients per group will provide 80% power to detect a 68% reduction in unplanned missed days and a 72% reduction in unplanned hospital admissions in the intervention group compared to the control group (2-sided test, significance level 0.05).

Aim 3

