Analysis. This aim focuses on estimating and testing the mediating effects of family CG self-efficacy on their anxiety at Time T4 and other time points. The analysis will follow a standard (Baron-Kenny) approach of first testing the associations between intervention and the mediator (self-efficacy), and between self-efficacy and the outcome (anxiety) controlling for the intervention. If both associations are significant, the indirect effect of the mediator is estimated as the difference in the intervention effect on the anxiety before and after adjusting for the mediator.¹⁰⁹⁻¹¹¹ The standard error of the indirect effect, used to construct a confidence interval, can be estimated using a marginal regression approach with standard generalized estimating equations software, or using a bootstrap approach.¹¹¹

Power. If the effect size (difference in means of intervention vs. control groups divided by within-group standard deviation) is 0.40 for anxiety at T4, and is 0.50 for CG self-efficacy at T4 and the correlation of self-efficacy and anxiety at T4 is 0.40, the difference in means in anxiety after adjusting for the self-efficacy is reduced to an effect size of 0.20 SDs (i.e., the indirect effect of self-efficacy is 0.20, or 50% of the total). Simulations with n=10,000 replications showed in this scenario that the proposed approach had 81% power for testing that the indirect effect is zero (two-sided test, significance level 0.05). Increasing the indirect effect by increasing either the correlation or the effect of the intervention on self-efficacy results in higher power.

Aim 4

Analysis. This aim examines if patient illness factors, care demands, demographic factors, and/or use of mental health interventions during treatment moderate the relationship between the intervention and CG outcomes. Effects of potential modifiers of the treatment effect will be examined by including terms for the modifier by treatment interaction effect in the basic ANCOVA model used to test the primary hypothesis.

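### Aim 3 names no baseline score for the self-efficacy/anxiety path, so if the intervention raises self-efficacy, non-causal correlation counts as mediation; adding T1 self-efficacy and T1 anxiety reduces this

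*Combined protocol and SAP*

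**What the plan says.** Section 6.0, Aim 3, follows the Baron-Kenny steps. It tests the effect of the intervention on self-efficacy, then the association "between self-efficacy and the outcome (anxiety) controlling for the intervention". If both are significant, the indirect effect is the change in the intervention effect on anxiety once self-efficacy enters the model. No T1 score or other covariate is named for either step, and nothing is said about confounding of the mediator-outcome path.

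The power scenario has a 0.40 SD effect on anxiety and an intervention effect that "is 0.50 for CG self-efficacy at T4 and the correlation of self-efficacy and anxiety at T4 is 0.40". From this it derives an indirect effect of 0.20 SD and 81% power. It adds: "Increasing the indirect effect by increasing either the correlation or the effect of the intervention on self-efficacy results in higher power".

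Two other aims identify their model. Aim 1 fits a mixed model "using baseline anxiety as a covariate, also adjusting for covariates described in Table 4". Aim 4 proceeds by "including terms for the modifier by treatment interaction effect in the basic ANCOVA model used to test the primary hypothesis". Aim 3 has no such reference. Table 4 (section 5.4) lists self-efficacy as the mediator, apart from the covariates. Section 5.2 has the Caregiver Inventory given at every time point, and section 4.0 places randomisation after the baseline measures.

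**The concern.** Randomisation protects the effect of the intervention on self-efficacy and the total effect on anxiety. It does not protect the link between self-efficacy and anxiety. Caregivers who are less confident at the outset may also be more anxious for reasons unrelated to the intervention. The team's descriptive study of 42 caregivers in colorectal cancer (section 1.2) points that way: lower self-efficacy for managing one's own health went with higher anxiety (p = .021; instrument and effect size not given).

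The plan's scenario treats the whole T4 correlation as causal. If part of it is not, and the intervention shifts self-efficacy, Aim 3 can report mediation that is partly or wholly an association present before the intervention. Both T1 scores are collected before randomisation, so they are valid covariates and could be used against this.

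**Working it through.** **Inputs from the documents.** 81 per arm; shift in self-efficacy 0.50 SD; T4 correlation 0.40; total effect 0.40 SD; T1-T4 correlation of anxiety 0.50 (Aim 1 power: "Assuming a correlation of 0.50 between CG anxiety scores at baseline and T4"). **Assumed.** T1-T4 correlation of self-efficacy 0.50; non-causal within-arm correlation 0.20, with other values below. Correlations are given as sizes, without sign.

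**1. The plan's figures.** Indirect effect = shift x path = 0.50 x 0.40 = 0.20 SD, or 0.20/0.40 = 50% of the total. This reproduces. The 81% power does not reproduce cleanly at 81 per arm: simulation gives 86% with a Sobel test and 89% with the two significance tests alone. Reading 0.40 as the overall rather than the within-arm correlation gives 82% with a bootstrap standard error, but the indirect effect is then 0.185. The plan states neither the exact test nor the simulated sample size. The point made here does not depend on this.

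**2. Size of the bias.** Unadjusted bias = shift x non-causal correlation.
- Shift 0.50: 0.50 x 0.20 = 0.10 SD.
- No shift: 0.

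**3. What T1 anxiety removes.** The remaining path coefficient is (r(S4,A4) - r(S4,A1) x r(A1,A4)) / (1 - r(S4,A1)²), with S for self-efficacy and A for anxiety.
- *Shared stable trait* (trait correlation 0.20/0.50 = 0.40, so r(S4,A1) = 0.20): (0.20 - 0.20 x 0.50)/(1 - 0.04) = 0.104. The bias is 0.50 x 0.104 = 0.052 SD. With both T1 scores it falls to 0.035 SD.
- *Own-score carry-over* (each T4 score depends only on its own T1 score; this needs a T1 correlation of 0.20/(0.50 x 0.50) = 0.80, so r(S4,A1) = 0.80 x 0.50 = 0.40): 0.20 - 0.40 x 0.50 = 0. T1 anxiety alone removes the bias.

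**4. How often mediation is declared when there is none** (simulation, 81 per arm, shift 0.50, non-causal correlation 0.20). The lower end requires both step tests and a Sobel test to be significant; the upper end requires the two step tests only.

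| Structure | Unadjusted | T1 anxiety only | Both T1 scores |
|---|---|---|---|
| Stable trait | 44-65% | 14-28% | 7-14% |
| Own-score carry-over | 43-64% | 2-5% | 2-4% |

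**5. Sensitivity, stable trait.**
- Non-causal correlation 0.10, shift 0.50: 10-21% unadjusted, 3-7% with both scores.
- Non-causal correlation 0.40, shift 0.50: 85-88% unadjusted, 40-55% with both.
- Correlation 0.20, smaller shifts, unadjusted: 22-43% at 0.35 SD, 6-18% at 0.20 SD, 1-3% at no shift.
- Pilot intervention arm (section 1.2, Table 1): (146.4 - 143.0)/23.5 = 0.14 SD, from 7 caregivers at 4 weeks after radiation. At this shift and correlation 0.20 the unadjusted rate is about 3-11%.
- With the extension, "the sample for the final analysis will be 214 dyads", or 107 per arm: correlation 0.20 and shift 0.50 give 65-80% unadjusted and 11-17% with both scores. A larger sample makes the unadjusted rate worse.

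**The case against.** The strongest reply is that the text does not say the intervention is the *only* control. The phrase is standard Baron-Kenny wording, and the only model the plan defines for the intervention effect on anxiety is Aim 1, which includes baseline anxiety. Carrying that model into Aim 3 is a natural reading. Under own-score carry-over it would leave essentially no bias, and T1 self-efficacy would add nothing. This stands, and for that reason the unadjusted rates should not be read as what the analysis will certainly do. It does not close the point. Aim 3 does not state the carry-over, T1 self-efficacy is absent even if it is assumed, and under a stable trait T1 anxiety alone still leaves 14-28%.

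The second reply is that the sizes rest on assumptions. This also stands. The documents give no T1 correlation between the two measures and no stability for self-efficacy. The 0.50 SD shift is a planning value. The pilot's 0.14 SD is a change within one arm; the control column is not visible in the extracted table, so 0.14 is not an estimate of the between-arm shift.

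A reader might infer from the 85-88% rate that a positive Aim 3 result would most likely be spurious. The documents do not support that. A fully non-causal 0.40 needs a trait correlation of 0.40/0.50 = 0.80. It cannot arise from own-score carry-over at these stabilities, where the ceiling is 0.50 x 0.50 = 0.25.

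**Conclusion.** The concern holds in a limited form. As written, Aim 3 names no baseline score for the mediator-outcome path, and no stated model includes T1 self-efficacy. If the intervention raises self-efficacy, the non-causal part of the T4 correlation is counted as mediation. At the plan's 0.50 SD shift and an assumed non-causal correlation of 0.20, the spurious indirect effect is 0.10 SD and mediation is declared in about 43-65% of trials unadjusted. How far T1 scores reduce this depends on the data structure: to 7-14% with both scores under a stable trait, or to about 2-5% with T1 anxiety alone under own-score carry-over. At a shift near 0.14 SD the problem is small.

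Two further inferences are not supported. The primary T4 contrast is not affected, because it compares randomised arms without conditioning on self-efficacy. Nor does baseline adjustment make the mediation estimate causal: unmeasured traits, confounders that change after baseline and reverse causation between two T4 measures all remain possible.

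**What to change.** 1. State in Aim 3 that both the mediator model and the outcome model include T1 self-efficacy and T1 anxiety.
2. State the mediation conclusion as conditional on no further mediator-outcome confounding, since the adjustment reduces it and may not remove it.
3. Rerun the 81% power figure for the adjusted model, naming the test and the sample size, with a range for the share of the 0.40 correlation that is pre-existing.
4. Optional good practice, not correction of an error: report how large a residual mediator-outcome correlation would have to be to bring the indirect effect to zero.

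The cost is SAP wording and one simulation; no new data are needed. The effect on power depends on the pre-existing share. With 81 per arm, a stable trait and T1-T4 correlations of 0.50, simulated power goes from unadjusted to adjusted as follows: no share, 86-89% to 94-95%; half, 84-88% to 81-90%; three quarters, 86-89% to 63-77%. The unadjusted ranges differ from each other only by simulation noise. The fall in the last case is largely removal of spurious signal. If none of the correlation is pre-existing, the adjusted estimate stays at 0.20 SD.

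### Aim 3 estimates the indirect effect only when both path tests are significant, so the reported effect is too large on average and a failed path leaves no planned estimate or interval

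*Combined protocol and SAP*

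**What the plan says.** Section 6.0, Aim 3 (Analysis) opens: "This aim focuses on estimating and testing the mediating effects of family CG self-efficacy on their anxiety at Time T4 and other time points". The procedure is a Baron-Kenny sequence, "first testing the associations between intervention and the mediator (self-efficacy), and between self-efficacy and the outcome (anxiety) controlling for the intervention". The next sentence sets the condition: "If both associations are significant, the indirect effect of the mediator is estimated as the difference in the intervention effect", taken before and after adjusting for the mediator. Then: "The standard error of the indirect effect, used to construct a confidence interval, can be estimated using a marginal regression approach", with a bootstrap as the alternative. This interval is attached to the conditional estimate.

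Neither the Aim 3 text, the closing summary of section 6.0, nor its model-building list says what is reported if one path is not significant.

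The Aim 3 power paragraph assumes an effect that "is 0.40 for anxiety at T4" and "is 0.50 for CG self-efficacy at T4 and the correlation of self-efficacy and anxiety at T4 is 0.40", from which "the indirect effect of self-efficacy is 0.20, or 50% of the total".

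**The concern.** The indirect effect is built from the two path coefficients. Computing it only when both have passed a significance test keeps the trials in which those coefficients came out large and drops the rest, so the estimates that get reported are too large on average. When a path fails, the plan offers no indirect effect and no interval, and a reader cannot tell absent mediation from mediation measured imprecisely.

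Self-efficacy is the stated mechanism of the intervention (section 1.2, Theoretical Framework), so how much of the effect it carries is the substance of the aim. Because the aim covers other time points as well as T4, the filter would act again at each visit, and only visits that pass would show an estimate. The problem is separate from when the mediator is measured and from confounding; it would remain if both were dealt with.

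**Working it through.** **Inputs.** From Aim 3 (Power): effect on self-efficacy a = 0.50 SD; self-efficacy/anxiety correlation 0.40, read as the within-arm slope b with SD 1; two-sided 0.05. From Aim 1 (Power): 81 per arm. From section 3.0 (Projected Enrollment): 214 in the final analysis, or 107 per arm if allocation is equal.

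**The plan's indirect effect.** a × b = 0.50 × 0.40 = 0.20, which is 50% of the 0.40 total. This reproduces the plan and supports the within-arm reading of the correlation.

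**Which test does the filtering.** The standard error of b is √[(1 − b²)/2n]. At 81 per arm it is √(0.84/162) = 0.072, so b/SE = 5.6 and that path almost always passes. The standard error of a is s = √(2/n): 0.1571 at 81 per arm and 0.1367 at 107. Path a passes when its estimate exceeds c = 1.96s: 0.308 and 0.268.

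**Formula.** The two path estimates are independent, so the inflation of a × b is close to that of a alone. With z = (c − a)/s, the pass probability is p = 1 − Φ(z) and the relative inflation is s·φ(z)/(p·a). The wrong-sign tail is negligible.

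**Plan scenario.**
- 81 per arm: z = (0.308 − 0.50)/0.1571 = −1.22; p = 0.889; inflation = 0.1571 × 0.189/(0.889 × 0.50) = 6.7%.
- 107 per arm: z = (0.268 − 0.50)/0.1367 = −1.70; p = 0.955; inflation = 0.1367 × 0.0945/(0.955 × 0.50) = 2.7%.

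**Range.** Only the first row uses the plan's values. The other effects are assumptions made here, and no row adjusts for baseline. The inflation column is from simulation (40,000 trials, two t-tests); the formula agrees to within about three percentage points.

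| a, b | True a × b | Pass, 81 / 107 per arm | Mean inflation, 81 / 107 per arm |
|---|---|---|---|
| 0.50, 0.40 (plan) | 0.20 | 89% / 95% | 7% / 3% |
| 0.36, 0.40 | 0.144 | 62% / 75% | 27% / 16% |
| 0.25, 0.40 | 0.10 | 36% / 45% | 65% / 48% |
| 0.20, 0.30 | 0.06 | 24% / 31% | about 100% / 78% |

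The last 107-per-arm pass rate takes path a alone (p = 0.31), because path b nearly always passes there too.

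**Without the condition.** The simulated mean in the plan's scenario is 0.200, so the estimator itself is unbiased. At 81 per arm the filter splits this into 0.2135 in the 88.6% of trials that pass and 0.094 in the 11.4% that do not: 0.886 × 0.2135 + 0.114 × 0.094 = 0.20.

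**Sensitivity to baseline adjustment.** Aim 3 does not say whether its models adjust for baseline. If they do, and the baseline correlation is 0.50 for both variables (an assumption here), the results at 107 per arm become: a = 0.50, pass 99%, inflation 1%; a = 0.36, 86%, 8%; a = 0.25, 56%, 34%.

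**The case against.** The strongest reply is that the harm is slight where the plan expects to be. At the current sample size the plan's scenario passes in about 95% of trials with 3% average inflation, and every material figure comes from effects the plan does not assume. That stands, and the smaller effects must be read as a range. In particular, 0.36 appears in the plan only as the detectable baseline-adjusted difference in anxiety; it is not a self-efficacy target. On the other side, nothing in the documents establishes 0.50 for self-efficacy at T4. The pilot table in section 1.2 shows one arm of seven caregivers moving from 143.0 to 146.4 with an SD near 24, which is not a between-arm effect and neither supports nor contradicts 0.50.

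A second reply is that both path models are fitted anyway, so the indirect effect could be recovered as the product of their coefficients. That is true. The defect is that the plan does not commit to reporting it, not that it cannot be obtained.

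A third is that the mediation conclusion would barely move. At 81 per arm in the plan's scenario, requiring both paths to be significant has 88–89% power and the percentile bootstrap 89%. That also stands; the gain is in estimation.

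A reader might infer that any indirect effect reported under this rule is an overestimate. The bias is in the average only: in the plan's scenario at 81 per arm, 47% of the estimates that pass still fall below the true 0.20. A reader might also take the statement that "the proposed approach had 81% power for testing that the indirect effect is zero" as bearing on the condition. It does not; that figure is a separate matter and nothing here depends on it.

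**Conclusion.** The point holds as a reporting and estimation defect in a secondary, mechanistic aim; the primary T4 anxiety comparison is untouched. As written, the rule conflicts with the aim's stated purpose of estimation. Its cost under the plan's assumptions is small: 7% average inflation with 11% of trials lacking an estimate at 81 per arm, and 3% with 5% at 107.

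The cost becomes material only if the true self-efficacy effect is below 0.50 SD. Over the range shown, average inflation is about 16% to 100%, and the condition fails in about 25% (1 − 0.75) to 76% (1 − 0.24) of trials. Those figures assume within-arm SD 1, equal allocation and no baseline adjustment, and they would be lower with adjustment. The absence of an estimate is most likely exactly when mediation is weaker than hoped, which is when an interval is most needed. Since the correction costs almost nothing, it should be made.

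**What to change.** In Aim 3 (Analysis), delete the condition that both associations be significant. State that the indirect effect, defined as now by the change in the intervention effect on adjusting for self-efficacy, is estimated and reported in all cases and at every time point analysed, with a percentile bootstrap 95% confidence interval. Conclude mediation only if that interval excludes zero. Report both path coefficients with their intervals beside it, as description and not as a precondition.

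The cost is a sentence or two of wording and a bootstrap the plan already permits; no extra data, visits or participants are needed. The downside is that an imprecise indirect effect will sometimes be reported when a path is weak. The interval will show that imprecision.
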